3.2 Secondary estimands

The secondary clinical questions of interest include:

- What is the effect of secukinumab 300 mg s.c. compared to placebo in the proportion of participants with moderate to severe RCT who achieve an improvement (increase) of at least 40 points from BSL in the WORC PSD at Week 16 regardless of discontinuation due to any reason, use of prohibited medication, or use of rescue medication?
- What is the effect of secukinumab 300 mg s.c. compared to placebo in the proportion of
 participants with moderate to severe RCT who achieve an improvement (increase) of at
 least 50 points from BSL in the WORC total score at Week 16 regardless of
 discontinuation due to any reason, use of prohibited medication, or use of rescue
 medication?
- What is the effect of secukinumab 300 mg s.c. compared to placebo in participants with moderate to severe RCT in change from BSL in the PROMIS-SF Upper Extremity score at Week 16 regardless of discontinuation due to any reason, use of prohibited medication, or use of rescue medication?
- What is the effect of secukinumab 300 mg s.c. compared to placebo in the proportion of participants with moderate to severe RCT who achieve an improvement (increase) of at least 40 points from BSL in the WORC PSD at Week 24 based on the Week 24 data available at the Week 16 DBL regardless of discontinuation due to any reason, use of prohibited medication, or use of rescue medication?
- What is the effect of secukinumab 300 mg s.c. compared to placebo in participants with moderate to severe RCT in change from BSL in the WORC PSD score at Week 24 based on the Week 24 data available at the Week 16 DBL regardless of discontinuation due to any reason, use of prohibited medication, or use of rescue medication?

The estimand definition of all secondary objectives related to change from BSL (e.g., change from BSL in PROMIS-SF Upper Extremity score) will have the same attributes as that for the primary estimand, except for the endpoint.

The estimand definition for the secondary objectives related to proportion (e.g., proportion of participants achieving certain amount of improvement from BSL in WORC PSD and WORC total score) is described by the following attributes:

- Population: defined through appropriate inclusion/exclusion criteria to reflect the targeted moderate to severe RCT population
- Endpoint: proportion of participants who achieve a certain amount of improvement from BSL in the variable of interest
- Treatment of interest: the randomized treatment (secukinumab or placebo)

The intercurrent events will be handled as follows:

- 1. Discontinuation of study treatment due to any reason (including AE and lack of efficacy): if participants discontinue study treatment due to any reason (including AE and lack of efficacy), the event will be ignored (treatment policy)
- 2. Prohibited medication: if participants receive prohibited medication without study treatment discontinuation, the event will be ignored (treatment policy)
- 3. Rescue medication: if participants take rescue medication without study treatment discontinuation, the event will be ignored (treatment policy)

Summary measure: difference in proportions between treatments

4 Study design

4.1 Overall design

The trial is designed as a randomized, double-blind, placebo-controlled Phase III study over 24 weeks in approximately 234 participants with moderate to severe RCT, refractory to SoC (NSAIDs course as per local standard practice, if not intolerant or contraindicated, and a course of physiotherapy over a period of 8 weeks).

The trial comprises the following periods:

Screening / run-in period

A screening period of up to maximum of 56 days will be used to assess participant eligibility. During this time, the participant can demonstrate that they are refractory to SoC. During the 2-week run-in period prior to the BSL visit, the participant will need to have 2 weeks of stable NSAID intake and standardized physiotherapy. This is important in order to ensure the participants are refractory to SoC and to establish compliancy with the stabilized dosing of NSAID treatment and physiotherapy regimen to be maintained throughout the study.

MRI will be performed during Screening period to exclude other shoulder pathologies and tears (if present) >50%. Evidence of tendinopathy should be established by a centrally read MRI. MRI performed within 3 months from baseline may be accepted if deemed suitable by the central reader.

Shoulder x-rays will also be performed in order to rule out other shoulder pathologies. Historic x-rays will be accepted if performed \leq 3 months prior to BSL.

Study period 1 (BSL to Week 16)

During Study period 1, double-blinded treatment is administered over 12 weeks, reflecting 16 weeks of total drug exposure. Approximately 234 eligible participants will be randomized at BSL in a 1:1 ratio to one of the following arms:

- Arm 1 (N=117): secukinumab 300 mg s.c. at Day 1 and Weeks 1, 2, 3, 4, 8, and 12
- Arm 2 (N=117): placebo at Day 1 and Weeks 1, 2, 3, 4, 8, and 12

The last dose of study treatment will be administered at Week 12; the primary outcome assessments will be performed at Week 16.

Randomization will be stratified by tear status (no tear/partial tear). Participants should continue on stable NSAID pain medication and a standardized physiotherapy regimen. Reduction in NSAID dose is permitted after BSL, but participants must not increase above dose established during run-in. Use of corticosteroid injections is not permitted during this time.

Study period 2 (Follow-up period)

A follow-up period of 8 weeks after the end of the treatment period is planned to assess the maintenance of effect and collect follow-up safety data up to Week 24. Investigator, site personnel, persons performing the assessments and participants will remain blinded, but Novartis clinical trial and submission teams will be unblinded after Week 16 readout. Participants should continue on stable NSAID therapy and physiotherapy during this period. Reduction in NSAID dose is permitted after BSL, but participants must not increase above dose established during run-in. Corticosteroid injections are also not permitted after Week 16.

Please refer to Section 6.8.2 for more information on medication prohibited throughout the course of study (up to Week 24). Refer to Section 1.2 for study design figure.

Off-site procedures

At the Investigator's discretion, participants may avail of home administration of study drug (self-administered or by a care-giver) at Week 1 and Week 3. Participant and/or caregiver would need to be trained and approved by Investigator for these administrations. Site should have confirmed contact with participant for these home administrations. Tele-visits, i.e., secure videoconferencing, between the Participant and Investigator or designated site staff may also be utilized to support administration of study drug at home.

4.2 Scientific rationale for study design

Table 4-1 Rationale for study design

Study Design Aspect	Rationale
Overall (double-blind, randomized, parallel-group, placebo-controlled)	The double-blind, randomized, parallel-group, placebo-controlled design used in this study is intended to enable the evaluation of treatment effect of the secukinumab 300 mg s.c. regimen compared to placebo.
Randomization (strata, allocation ratio)	All eligible participants will be randomized via Interactive Response Technology (IRT) to one of the treatment arms at a 1:1 ratio. Stratification factor of partial or no tear will be included.
Blinding	Double-blinding is used in this study to minimize bias in the evaluation of safety and efficacy. Blinding is maintained beyond the primary endpoint for Investigator, site personnel, persons performing the assessments and participants, but Novartis clinical trial and submission teams will be unblinded after the Week 16 readout.

Study Design Aspect	Rationale
Use of Placebo	Treatment with placebo is justified to ensure reliable evaluation of the efficacy and safety of the active treatment in light of the nature of the condition and the outcome measures used.
Duration of study periods	A 16-week treatment duration (last dose administered at 12 weeks) was chosen as this is considered a reasonable treatment duration with a biologic for non-acute RCT. The primary endpoint of the trial is assessed at Week 16, 4 weeks following the last injection of study treatment. The follow-up period after the end of study treatment is included to generate data to assess maintenance of the treatment effect and to collect treatment safety follow-up data in this indication.

The study will enroll participants with moderate to severe symptomatic RCT with inadequate response (refractory) to physiotherapy, NSAIDs, or local subacromial corticosteroid injection, or intolerance to NSAIDs or local corticosteroid injection. The last corticosteroid therapy must have been ≥ 12 weeks prior to randomization. Participants must be naïve to IL-17 inhibition therapy.

The participant population with RCT was chosen as this is one of the most frequent tendinopathies. Tendinopathy most commonly presents during adulthood from 18 up to 65 years of age, as incidence is rare in adolescent and pediatric populations Zbojniewicz et al 2014. Moreover, the clinical evidence for a role for IL-17 in the pathogenesis of tendinopathy has so far only been shown for RCT and has not been investigated for other tendinopathies (Millar et al 2017).

Participants with a symptom duration of ≥ 6 weeks and ≤ 6 months based on medical convention will be identified, where an acute condition may be defined as up to 6 weeks in duration from onset and a chronic condition would be expected to persist beyond 6 months. Evidence of the early biological involvement of IL-17A in this disease process can be seen in preclinical models (data on file):

- Increased IL-17A mRNA and protein expression level previously noted in early human tendinopathic biopsies (Millar et al 2016)
- IL-17A high-expressing tendon-resident immune cells were most prevalent in early versus late human tendinopathy biopsies (Millar et al 2016), whileIL-17A blockade significantly improved tendon structure and function in a rodent model of supraspinatus tendinopathy that is, by definition, a model of early disease (Millar et al 2018).

In addition, the post-hoc exploratory analyses conducted on data from the Phase II PoC trial CAIN457X2201 support these assumptions, as participants with symptom duration greater than 6 months did not appear to benefit from secukinumab treatment.

The definition of participants with moderate to severe symptoms in the proposed Phase III trial is supported by the inclusion of average weekly pain NRS \geq 5 (on a scale from 0 to 10) in the eligibility criteria, which corresponds to a moderate to severe pain level (Jensen et al 2017), in combination with WORC \leq 40 (normalized to a 100-point scale where 100 points is symptom free and 0 indicates worst symptoms). It became evident from the analyses of the CAIN457X2201 study that applying more stringent selection criteria would lead to the inclusion of a participant population more likely to benefit from secukinumab treatment.

The study participant population is enrolled with a Baseline WORC Total of \leq 40 points, representing a disease severity ranging from moderate to severe. This cut-off is intended to match the same severity range defined by physicians using the PhGA tool. According to clinicians with experience using the PhGA scale, as well as references in the literature (Harrington 2009), PhGA values below 40 are representative of milder symptoms, whereas values above 50 are clearly indicative of moderate disease, with higher values representing severe disease. Therefore, a cut-point of 50 points on PhGA VAS was used to classify Phase II POC study participants into two distinct groups: PhGA VAS \leq 50 to define participants with mild disease and PhGA VAS \geq 50 to define participants with moderate to severe disease. Using receiver operator characteristic curve analysis (Phase II POC study), a WORC Total score of 40 was identified as the optimal cut-off to discriminate mild participants from those with moderate to severe disease based on the PhGA VAS. Special attention is given to minimizing the probability of enrolling participants with mild tendinopathy in the proposed study, to favor targeting those most likely to benefit from the intervention under investigation.

A pain score of ≥ 5 (on a scale from 0 to 10) on NRS to denote inadequate control of pain is justified based on a study in a broad sample of participants with rheumatological as well as mechanical musculoskeletal conditions (Falgarone et al 2005), in which the median level of pain requiring analgesic intake as judged by the participants was 48, with a mean of 51.56 on a 100 mm VAS, which would equate to a score of 5 on NRS.

An upper age limit of 65 years at randomization is set based on the expectation that treatment with an IL-17A inhibitor will not target aging-related root causes of RCT in an elderly population. Tendons have been shown to undergo structural changes with age, such as glycosaminoglycan infiltration, fibrocartilaginous change, calcification, blood vessel wall thickening, and tenocyte loss (Chard et al 1994). Moreover, the healing response has been shown to be impaired due to a slower metabolic rate in aged tenocyte-like cells (Klatte-Schulz et al 2012). Hence, treatment with secukinumab may have a lower likelihood of providing efficacy in patients of advanced age.

4.3 Justification for dose

Both doses of secukinumab 150 mg and 300 mg have been approved for use across several indications. A loading dose of 150 mg every week for the first 4 weeks followed by maintenance dosing once every 4 weeks thereafter is recommended for treating nr-axSpA. A starting dose of 150 mg every 4 weeks (which may include a weekly loading regimen over the initial 4 weeks) has been recommended for PsA and AS, but can be increased to 300 mg if disease remains active. The recommended dose for plaque psoriasis in adults is a weekly loading regimen of secukinumab 300 mg for the initial 4 weeks and maintenance dosing every 4 weeks thereafter at the same dose. Thus, despite the approval of both the 150 mg and 300 mg dose options for PsA and AS, the 300 mg regimen provided greater efficacy across multiple domains in PsA (study CAIN457F2312) and in AS (study CAIN457F2314).

The enthesis can be considered analogous to tendon tissue in terms of biomechanical load and in the pathological processes in inflammatory disease (Benjamin, McGonagle 2009). In PsA study CAIN457F2312, the LEI showed numerically better improvements in the 300 mg group compared to the 150 mg group. Furthermore, in AS study CAIN457F2314, the MASES score

Page **37** of **107** Protocol No. CAIN457O12301

also showed numerically better outcomes at longer-term timepoints in the 300 mg group compared to 150 mg.

The safety profile of secukinumab showed no overall dose dependency across multiple indications including PsA, AS, nr-axSpA, and psoriasis; an exception is *Candida* infections (mainly non-serious, localized mucosal or cutaneous candidiasis), which have been more frequent in the 300 mg regimen compared to 150 mg regimen (PSUR 2020). Moreover, the safety results from the Phase II study CAIN457X2201 were consistent with previous secukinumab studies. Thus, the cumulative safety data collected from clinical studies and post-marketing data support a consistent safety profile for secukinumab and the use of the proposed 300 mg s.c. dose, with 5x weekly initial loading up to Week 4, and two additional doses at Weeks 8 and 12.

4.3.1 Rationale for choice of background therapy

NSAIDs (AxMP: Auxiliary Medicinal Product): Current drug therapy SoC for management of RCT symptoms, alongside physiotherapy, is limited to NSAIDs. During the 2-week run-in period, participants should take NSAIDs at a stable dose and still have inadequate control of symptoms at randomization in order to participate in the study. Alternatively, NSAID use should have been stopped in participants who are intolerant or who have contraindications. Participants who tolerate NSAIDs will continue taking their stable NSAID regimen from the run-in period until Week 24. A stable NSAID dosing regimen during the treatment period and up to the primary outcome assessment at Week 16 is intended to avoid confounding the treatment effect of secukinumab on the tendinopathy. Participants may decrease their dose after BSL and are permitted to subsequently return to the dose that was established during run-in period. However, the dose of NSAID should not increase above that established during the run-in. It is also maintained throughout the 8-week follow-up period in order to establish the maintenance of effect is not affected by a change of NSAID dosing regimen. Any changes to NSAID type and/or increase in dose will be recorded as a deviation to the protocol, but would not result in study treatment discontinuation or withdrawal of the participant.

Corticosteroid use: If participants received previous corticosteroid injections in the affected shoulder, these must have been given ≥ 12 weeks prior to randomization (no more than 2 injections). During the 16-week treatment period, local corticosteroid injection is not allowed. The avoidance of corticosteroid injections up to the primary outcome assessment at Week 16 is intended to avoid confounding the treatment effect of secukinumab on the tendinopathy. Participants are not permitted to receive a corticosteroid injection after Week 16 in order not to confound the evaluation of maintenance of effect 8 weeks after the end of the treatment period.

4.4 Rationale for choice of control drugs (comparator/placebo) or combination drugs

The placebo effect in interventional trials in the treatment of RCT is considerable (as also observed in the Phase II study CAIN457X2201); hence, a placebo control is warranted. All participants (both study treatment arms) will in addition receive SoC (NSAIDs, physiotherapy). Blinding of Investigator, site personnel, persons performing the assessments, participants and sponsor up to the primary outcome assessment at Week 16 allows for an unbiased assessment of subjective readouts such as efficacy parameters (especially the PROs) and also for AEs

Page **38** of **107** Protocol No. CAIN457O12301

evaluation. The blinding is maintained for Investigator, site personnel, persons performing the assessments and participants beyond the primary endpoint until the end of the 24-week study to ensure reliable efficacy and safety assessments. Novartis clinical trial and submission teams will be unblinded after Week 16 readout.

4.5 Rationale for public health emergency mitigation procedures

In the event of a public health emergency as declared by local or regional authorities (i.e., pandemic, epidemic or natural disaster), mitigation procedures may be required to ensure participant safety and trial integrity and are listed in relevant sections of the study protocol. Notification of the public health emergency should be discussed with Novartis prior to implementation of mitigation procedures, and permitted/approved by local or regional health authorities and ethics committees as appropriate.

4.6 Purpose and timing of interim analyses/design adaptations

The primary endpoint analysis will be performed after all participants have completed the visit at Week 16 or discontinued earlier in order to support regulatory filings.

Novartis clinical trial and submission teams will be unblinded following the primary endpoint analysis database lock, but Investigator, site personnel, persons performing the assessments and participants will remain blinded. At the end of the study, the final CSR analysis of all data collected will be performed when all participants have completed their last study visit. The Investigators, site personnel and participants will remain blinded until final database lock.

4.7 End of study definition

Study completion is defined as when the last participant finishes their last study visit (at Week 24), and any repeat assessments associated with this visit have been documented and followed-up appropriately by the Investigator (e.g., each participant will be required to complete the study in its entirety and thereafter no further study treatment will be made available to them in the scope of the trial).

All randomized and/or treated participants who a) discontinue study treatment and do not return for remaining scheduled visits or EOS, or b) discontinue study and do not come in for final evaluation (EOT) should have a safety follow-up call conducted 60 days after last administration of study treatment. A safety follow-up call is only necessary for all participants who discontinued the trial. The information is kept as a source documentation. SAE reporting continues during this time period as described in Section 8.6.3.

5 Study population

The target population is to consist of male and non-pregnant non-nursing female participants at least 18 years of age, but less than or equal to 65 years of age at the time of randomization, with a diagnosis of unilateral RCT, with symptoms present for at least 6 weeks but not more than 6 months at BSL. 234 participants to be enrolled.

Participants must have been refractory to standard of care: NSAIDs course as per local standard practice (if not intolerant or contraindicated) and a course of physiotherapy over a period of 8 weeks, as defined in the inclusion criteria. This can be incorporated into the 8 week screening period. Participants should also have had at least 2 weeks of a standardized physiotherapy treatment prior to BSL, as well treatment with a stable NSAID regimen (unless intolerant or contraindicated). Participants should avoid performing activities that could induce further pain or injury. Participants must have no tendon tear or if there is a tear, it must be a partial thickness tear with ≤50% thickness tear and maximum AP diameter of 10mm. The study sample should have a maximum of 50% of participants with a partial tear as established by MRI during screening. Evidence of tendinopathy on a centrally read MRI should also be established. MRI performed within 3 months from baseline may be accepted if deemed suitable by the central reader. Bilateral shoulder x-rays will also be required in order to rule out other shoulder pathologies as listed in exclusion criteria. Historic image may be accepted if performed ≤3 months prior to BSL.

Participants must have an average weekly pain score on NRS \geq 5 (corresponding to moderate to severe pain on a 0-10 point scale where 10 indicates worst pain) during the past 7 days in the week prior to BSL, nocturnal pain in shoulder on at least 3 out of 7 nights in the week prior to BSL or a positive painful arc test on examination, in combination with WORC score \leq 40 (where 100 points is symptom-free and 0 is worst symptoms) at Screening and BSL.

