Participants who **disagree to continue attending all remaining study** visits after prematurely discontinuing the study treatment (including those who initially continued to attend site visits but subsequently decided to discontinue the study) should perform an end of treatment visit, 4 weeks after their last study treatment administration (or as soon as possible upon the decision of study discontinuation if more than 4 weeks elapsed since last dose of study treatment). A corresponding end of study post-treatment safety follow up visit should be performed 12 weeks after the last administration of the study treatment (or as soon as possible, if more than 12 weeks elapsed since last dose of study treatment).

If the participant cannot or is unwilling to attend any visit(s), the site staff should maintain regular telephone contact with the participant, or with a person pre-designated by the participant. This telephone contact should preferably be done according to the study visit schedule.

After discontinuation from study treatment, at a minimum, in abbreviated visits, the following data should be collected at clinic visits or via telephone/email contact:

- New / concomitant treatments
- AEs / Serious Adverse Events

The Investigator must also contact the IRT to register the participant's discontinuation from study treatment.

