7.2 Participant discontinuation from the study

Discontinuation from study is when the participant permanently stops receiving the study treatment, and further protocol-required assessments or follow-up, for any reason.

If the participant agrees, a final evaluation at the time of the participant's study discontinuation should be made as detailed in Section 1.3 Schedule of Activities.

Participants who are prematurely withdrawn from the study will not be replaced.

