7.3 Withdrawal of informed consent and exercise of participants' data privacy rights

Withdrawal of consent/opposition to use of data and/or biological samples occurs in countries where the legal justification to collect and process the data is consent and when a participant:

- Explicitly requests to stop use of their data
- and
- No longer wishes to receive study treatment

and

• Does not want any further visits or assessments (including further study-related contacts)

This request should be as per local regulations (e.g., in writing) and recorded in the source documentation.

Withdrawal of consent impacts ability to further contact the participant, collect follow-up data (e.g. to respond to data queries) and potentially other country-specific restrictions. It is therefore very important to ensure accurate recording of withdrawal vs. discontinuation based on the protocol definitions of these terms.

In this situation, the Investigator should make a reasonable effort (e.g., telephone, e-mail, letter) to understand the primary reason for the participant's decision to withdraw their consent/exercise data privacy rights and record this information. The Investigator shall clearly document if the participant has withdrawn his/her consent for the use of data in addition to a study discontinuation.

Study treatment must be discontinued and no further assessments conducted, and the data that would have been collected at subsequent visits will be considered missing.

Further attempts to contact the participant are not allowed unless safety findings require communicating or follow-up.

If the participant agrees, a final evaluation at the time of the participant's withdrawal of consent/exercise data privacy rights should be made as detailed in Section 1.3 Schedule of Activities.

Further details on withdrawal of consent or the exercise of participants' data privacy rights are included in the corresponding informed consent form.

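### The Section 4.7 safety call falls 24 days before the 84-day safety window closes; the gap is clearest for a participant who takes the Week 12 dose and then leaves

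*Protocol*

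**What the plan says.** Protocol Section 4.7 covers two groups: (a) participants who discontinue study treatment and do not come back for their remaining visits, and (b) participants who discontinue the study and do not attend the final evaluation. Both "should have a safety follow-up call conducted 60 days after last administration of study treatment". The section adds that "SAE reporting continues during this time period as described in Section 8.6.3".

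The other post-dose safety provisions use a longer period. Section 8.6.1 asks for AE monitoring for at least 12 weeks after last dose. Section 8.6.3 requires every SAE up to 12 weeks after last dose to be reported. Protocol 9.4.2 and SAP 2.7 and 2.7.1 count events up to last dose + 84 days as on-treatment.

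Section 7.1 deals with participants who decline further visits after stopping treatment prematurely, including those who attend for a while and then leave the study. It says: "A corresponding end of study post-treatment safety follow up visit should be performed 12 weeks after the last administration of the study treatment". If a participant cannot or will not attend, "the site staff should maintain regular telephone contact with the participant", and "This telephone contact should preferably be done according to the study visit schedule". It sets new or concomitant treatments and AEs/SAEs as the minimum data for contacts after treatment discontinuation.

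Section 7.2 defines leaving the study more broadly: "Discontinuation from study is when the participant permanently stops receiving the study treatment, and further protocol-required assessments or follow-up, for any reason". Under Section 7.3, after withdrawal of consent, "Further attempts to contact the participant are not allowed unless safety findings require communicating or follow-up".

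**The concern.** Section 4.7 is where a site would look for the closing contact with a participant who does not return, and its date is earlier than the end of the period over which events count. It does not cross-refer to Section 7.1. A site that treats the Day 60 call as its last contact can miss an event that starts 61 to 84 days after last dose, although the SAP would classify that event as treatment-emergent.

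Crude incidence (SAP 5.4.2.1) is the number of participants with the event divided by all participants at risk. Someone followed for 60 days after last dose therefore counts the same as someone followed for 84, and missed events bias the crude rate downwards. Exposure-adjusted rates are less affected, because SAP 2.4.1 ends exposure at the last visit when that comes before last dose + 84 days.

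**Working it through.** **Inputs.** Safety call: 60 days after last dose (Protocol 4.7). Window: 12 weeks (8.6.1, 8.6.3), or 84 days (9.4.2, SAP 2.7). Dose days: 1, 8, 15, 22, 29, 57, 85. Later visit days: 113, 141, 169 (Table 1-2).

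**The plan's own figure.** 12 x 7 = 84 days. The schedule agrees: Week 12 (Day 85) to Week 24 (Day 169) is 169 - 85 = 84 days. The 12-week and 84-day statements are therefore consistent, and the 60-day call is the exception.

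**The gap.** 84 - 60 = 24 days (post-dose Days 61 to 84), whichever dose was last. Call day = last-dose day + 60; window end = last-dose day + 84. The treatment-emergent window runs from Day 1 to the window end, so its length in days equals the window-end day, and the unobserved share is 24 divided by that length.

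| Last dose | Dose day | Call day | Window end | First scheduled visit at or after window end (days post-dose) | 24 days as share of window |
|---|---|---|---|---|---|
| Baseline | 1 | 61 | 85 | Day 85 (84) | 24/85 = 28.2% |
| Week 1 | 8 | 68 | 92 | Day 113 (105) | 24/92 = 26.1% |
| Week 2 | 15 | 75 | 99 | Day 113 (98) | 24/99 = 24.2% |
| Week 3 | 22 | 82 | 106 | Day 113 (91) | 24/106 = 22.6% |
| Week 4 | 29 | 89 | 113 | Day 113 (84) | 24/113 = 21.2% |
| Week 8 | 57 | 117 | 141 | Day 141 (84) | 24/141 = 17.0% |
| Week 12 | 85 | 145 | 169 | Day 169 (84) | 24/169 = 14.2% |

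**Early stoppers (last dose Baseline to Week 8).** Section 7.1 applies. If the 12-week visit takes place, or the telephone contact is kept on the visit schedule, a contact falls at 84 days or later in every row and the gap is 0 days. It becomes 24 days only if that contact lapses and the Section 4.7 call is the last one.

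**Full-course leavers (last dose Week 12).** Section 7.1 asks for its 12-week visit after premature discontinuation of study treatment. A participant who has had all seven injections has no dose left to stop, although the Week 16 visit is labelled end of treatment, so whether Section 7.1 applies is open to argument. If this participant leaves before Week 16 and skips the final evaluation, Section 4.7(b) and Section 7.2 apply. The only later contact clearly specified is the call on Day 145, and Days 146 to 169 have none.

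**The case against.** The strongest reply is that the provisions can all be followed together. Section 4.7 does not say that the Day 60 call is the last contact or that it ends AE collection, and it points to Section 8.6.3, which runs 12 weeks. Section 7.1 fixes a 12-week visit, expressly includes people who leave the study after stopping treatment, and falls back on telephone contact with AEs/SAEs as minimum data. A site that closed at Day 60 would be departing from Sections 7.1, 8.6.1 and 8.6.3.

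Most of this stands. A reader might infer from Section 4.7 that nobody who stops early has a safety contact planned after Day 60, or that AEs and SAEs from Days 61 to 84 need not be recorded. The documents support neither reading: Section 7.1 plans later contact for early stoppers, and recording through 12 weeks is required.

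Two things survive. The 12-week contact in Section 7.1 is an attended visit, which a participant who does not return will miss, and its telephone substitute is only preferably on schedule. Section 7.1 also does not clearly reach someone who finished dosing and then left. For that person, Sections 8.6.1 and 8.6.3 set the period for monitoring and reporting, but no contact is scheduled at its end.

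It is also fair to say that crude incidence ignores unequal follow-up for any dropout, not only here, and that termination leaves little for an amendment to improve.

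**Conclusion.** The point holds as a minor design inconsistency. The Section 4.7 call is 24 days short of the window that the rest of the plan uses. For early stoppers the practical gap is 0 days if Section 7.1 is followed on schedule, and 24 days if that contact lapses. For a participant who takes the Week 12 dose and leaves without the end-of-treatment visit, the plan as written leaves the last 24 of 169 days (14.2%) without a specified contact.

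This assumes nominal visit days and reads premature discontinuation in Section 7.1 as stopping before the last planned injection. If the sponsor reads it as anything before Week 16, the full-course leaver is covered too and only the wording needs repair.

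The documents do not say how many participants fall in either group, so no number of missed events can be given. The primary endpoint, sample size and power are unaffected. SAP Section 1 reports 21 randomized and 2 completed at termination, which limits the practical effect but does not make the 60-day rule right.

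**What to change.** In Section 4.7, require the final safety call at 84 days (12 weeks) or later after last dose, for both groups (a) and (b), and cross-refer to Section 7.1. Keep the Day 60 call as an interim contact if wanted, so that the earlier check is not lost and the recall period is not lengthened. State that participants who withdrew consent stay under Section 7.3.

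The cost is a short amendment and at most one extra call per participant: none where a contact at Day 84 or later is already made, one where the Day 60 call is kept and a final call is added. Section 10.1.8.1 asks for IRB/IEC approval of amendments, whereas Amendment 1 was classed as non-substantial with no prior approval needed, so the sponsor should state which route applies.

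Timing limits the benefit in this trial. With the maximum 56-day screening and nominal visits, a participant screened on 7 May 2024 reaches baseline on 2 July, the Week 12 dose on 24 September, the 60-day call on 23 November and Day 84 on 17 December 2024. That last date is 20 days after the latest SAP history entry (27 November 2024). If follow-up has closed, an optional listing of the day of last AE contact relative to last dose, for each participant who stopped or left early, would show any crude rate that rests on less than 84 days.
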